12.3 Concomitant Medications

Concomitant treatments are medications, other than trial medications, which are taken by subjects any time on- trial (on or after the first day of study treatment for each subject) or within 30 days for Arm A and 35 days for Arm B after last dose of trial treatment. Medications started after 30 (resp. 35) days will be presented and flagged in listings but will not be taken into account in summary tables.

Concomitant medications will be summarized from the “Concomitant medications” eCRF page. The ATC-2nd level and PT will be tabulated as given from the most recent available version of WHO-DD, Sept. 2016 or later. If multiple ATC can be assigned to a drug, all ATCs will be reported.

In case the date values will not allow to unequivocally allocate a medication to concomitant medication, the medication will be considered as concomitant medication (see section 9 for incomplete or missing dates).

Concomitant medications will also be listed. The listing will include: subject identification number, formulation, dose level and all corresponding collected data-fields on the corresponding eCRF page.

12.4 Concomitant Procedures

Concomitant procedures are procedures which are undertaken any time on- trial or within 30 days for Arm A and 35 days for Arm B after last dose of trial treatment. These will be listed according to the CRF page “Concomitant Procedures”. Procedures started after 30 (resp. 35) days will be presented and flagged in listing.

In case the date values will not allow to unequivocally allocate a procedure to concomitant procedure, the procedure will be considered as concomitant procedure (see section 9 for incomplete or missing dates).

The listing will include: subject identification number, formulation, dose level and all corresponding collected data-fields on the corresponding eCRF page.

12.5 Anti-cancer post-treatment

Anti-cancer post-treatments will be listed according to eCRF page “Anti-cancer treatment after discontinuation”. The listing will include: subject identification number, formulation, dose level and all corresponding collected data-fields on the corresponding eCRF page.

Anti-cancer post-surgeries and post-radiotherapies will also be listed according to eCRF pages “Anti-cancer surgeries after discontinuation” and “Anti-cancer radiotherapy after discontinuation”.

13 Treatment Compliance and Exposure

Population: SAF Analysis Set

Treatment compliance and exposure will be listed and summarized by dose level and overall using SAF Analysis set.

All dosing calculations and summaries will be based on “MSC2490484A Administration”, “Radiotherapy Administration” and “Cisplatin Administration” eCRF pages.

In Phase Ia, subjects will receive treatment with M3814 at a starting dose of 100 mg QD for Arm A and 50 mg QD for Arm B, which will be given 1.5 hours before each RT fraction (3 Gy) for up to 10 fractions (Arm A) or 2 Gy for 33 to 35 fractions (Arm B). In addition, in Arm B, on Fraction Days 1 and 31 for the 100 mg/m² dose, or weekly for the 40 mg/m² dose, cisplatin will be given after oral intake of M3814 and before RT is started. Dose escalation will continue up to a maximum dose of M3814 800 mg/day.

Number of treatment administrations

The number of fraction days of treatment will be summarized for Radiotherapy by dose level and overall.

CONFIDENTIAL
INFORMATION

24/60

The number of days of treatment will be summarized for M3814 by dose level and overall.

The number of infusions of Cisplatin will be summarized for both treatment schedules: 100 mg/m² twice (FD1, FD31) or 40 mg/m² weekly.

Cumulative dose

The cumulative dose (mg) of M3814 will be calculated as the sum of the total daily doses that the subject received.

The cumulative dose (Gy) of RT will be calculated as the sum of the total daily doses that the subject received.

The cumulative dose (mg/m²) of cisplatin per subject is the sum of the total dose that the subject received at each visit. At a given visit, the total dose (mg/m²) received is derived as:

$$\text{Total dose} = \text{Total dose administered (mg)} / \text{recalculated BSA (m}^2\text{)}$$

The recalculated BSA is derived based on formula described in section 11.3, using weight measured at the corresponding visit. In case the weight measurement is missing, the weight measurement closest to the administration date will be used. If there are two measurements which are equal distance away from the missing measurement, the earliest measurement will be used.

Compliance with treatment

The relative dose intensity with the treatment is defined as:

- For M3814:

$$\text{Relative dose intensity (\%)} = \left(\frac{\text{cumulative dose (mg)}}{x * \text{planned daily dose (mg)}} * 100 \right)$$

- For RT:

$$\text{Relative dose intensity (\%)} = \left(\frac{\text{cumulative dose (Gy)}}{x * \text{planned daily dose (Gy)}} * 100 \right)$$

Where :

- For Arm A: x = 10
- For Arm B:
 - o x = 35 if subject received less than 33 FD, to generate the maximum possible denominator for patients with incomplete dosing

- x = actual number of FD if subject received from 33 to 35 FD
- For Cisplatin:

$$\text{Relative dose intensity (\%)} = \left(\frac{\text{cumulative dose (mg)}}{\text{cumulative planned dose (mg)}} * 100 \right)$$

Where cumulative planned dose (mg) is the sum of planned dose at each visit. At a given visit, the planned dose (mg) is derived as:

$$\text{Planned dose} = \text{Planned dose (mg/m}^2\text{)} * \text{recalculated BSA (m}^2\text{)}$$

The recalculated BSA is derived based on formula described in section 11.3, using weight measured at the corresponding visit. In case the weight measurement is missing, the weight measurement closest to the administration date will be used. If there are two measurements which are equal distance away from the missing measurement, the earliest measurement will be used.

The relative dose intensity with the treatments will display using the following categories:

- > 100%
- [80% - 100%]
- [65% - 80%[
- [50% - 65%[
- < 50%

The following summary tables will be provided for M3814 and RT administrations by dose level:

- Number of days of M3814
- Number of FD of RT

Number of infusions of Cisplatin (separately for weekly/twice schedule)

- Cumulative dose of M3814 (mg)
- Cumulative dose of RT (Gy)
- Cumulative dose of Cisplatin (mg/m²)
- Relative Dose Intensity

The listing of exposure assessments (including e.g. date and time of administration, dose, frequency, change in dose) will be provided by subject as recorded from the related eCRF pages and for each M3814, RT and Cisplatin administration.

In addition, a summary listing will be provided with the cumulative dose, the relative dose intensity and the number of fraction days with treatments for each subject and treatment.

In addition, a listing of accountability for M3814 according to page “M3814/Placebo accountability” of eCRF will be produced. This listing will include the subject identification number, and all collected fields of the corresponding eCRF Page.

14 Efficacy Analyses

Secondary efficacy endpoints include Best Overall Response (BOR) and tumor measurements. Tumor assessments are based on local evaluations by the investigator according to RECIST 1.1 criteria. Local evaluations of target, non-target and new lesions are used to derive the BOR.

14.1 Best Overall Response

Population: FAS Analysis Set

The Best Overall Response (BOR) will be defined as the best response per RECIST 1.1 across all time points until determination of Progressive Disease (PD) or cut-off date, using the Investigator reported overall response per time point and excluding assessments after tumor surgery.

BOR will be defined as the best response across all time points (for example, a subject who has stable disease (SD) at the first assessment, partial response (PR) at the second assessment, and PD at the last assessment has a BOR of PR). The order to obtain the BOR is the following: complete response (CR), Partial Response (PR), Stable Disease (SD), Progressive Disease (PD), Not Evaluable (NE).

When SD is believed to be the best response, it must also meet the protocol-specified minimum 6 weeks (42 days) from first day of treatment. If the minimum time is not met, the subject's best overall response depends on the subsequent assessments. For example, a subject who has SD at the first assessment, PD at the second assessment and does not meet the minimum duration for SD, will have a best overall response of PD. The same subject lost to follow-up after the first SD assessment would be considered NE for BOR.

If a subject has missing baseline tumor assessment and/or no tumor assessment on-treatment, BOR will be NE.

The confirmed BOR will be also analyzed. In this case, CR and PR need to be confirmed at a subsequent assessment, at least 4 weeks after initial overall response assessment of CR/PR. Confirmed BOR will be derived as described in RECIST 1.1 guidance.

Overall response first time point	Overall response subsequent time point*	Confirmed BOR
CR	CR	CR
CR	PR	SD, PD or PR ^a
CR	SD	SD, if minimum criteria for SD duration met at first time point. Otherwise PD
CR	PD	SD, if minimum criteria for SD duration met at first time point. Otherwise PD
CR	NE	SD, if minimum criteria for SD duration met at first time point. Otherwise NE
PR	CR	PR
PR	PR	PR
PR	SD	SD
PR	PD	SD, if minimum criteria for SD duration met. Otherwise PD
PR	NE	SD, if minimum criteria for SD duration met. Otherwise NE
NE	NE	NE

* Subsequent time point is not necessarily the direct subsequent scan (eg. PR-SD-PR will have PR as confirmed BOR)

a If a CR is truly met at first time point, then any disease seen at a subsequent time point, even disease meeting PR criteria relative to baseline, makes the disease PD at that point (since disease must have reappeared after CR). Best response would depend on whether minimum duration for SD was met. However, sometimes 'CR' may be claimed when subsequent scans suggest small lesions were likely still present and in fact the patient had PR, not CR at the first time point. Under these circumstances, the original CR should be changed to PR and the best response is PR.

To analyze tumor response, it may be necessary to determine the date of tumor assessment, e.g. to check whether SD was asserted after a suitable time limit after baseline. In case of different dates of scans within the same tumor assessment, the earliest scan date is used as the date of tumor assessment.

Both Confirmed and Unconfirmed BOR will be summarized by tabulating the number and percentage of subjects with CR, PR, SD, PD or NE as BOR. In addition, confirmed objective response (confirmed BOR of CR or PR), unconfirmed objective response (unconfirmed BOR of CR or PR and disease control will be summarized. Objective response rate (ORR) and disease control rate (DCR) are indicated together with exact Clopper-Pearson 95%-confidence intervals (Clopper & Pearson, 1934).

The listing of tumor assessments (including e.g. lesion number, description and site, type of lesion, imaging date, assessment method, diameter (mm), sum of diameter of target lesions, BOR (confirmed and unconfirmed) will be provided by subject as recorded from the "Target Lesions", "Sum of Diameters", "Non-Target Lesions", "New Lesions" and "Assessment of disease based on imaging" eCRF pages.

A spider plot will display the percentage change from baseline in sum of longest diameter of target lesion against the date for each subject.

A swimmer plot displaying some key radiological milestones will be produced for each dose level separately. For each subject, the time from treatment start until end of follow-up will be represented (from treatment start to last date known to be alive or date of death). In addition, following information will be displayed: time to best overall unconfirmed response (CR, PR or SD), time to progression and status at the end of the follow-up (alive or dead).

For subjects alive, the following dates will be used to determine the last date known to be alive prior or at data cut-off.

- All patient assessment dates:
 - Laboratory assessments using information from “Serology”, “Hematology”, “Biochemistry”, “Coagulation”, “Urinalysis”, “Microscopic analysis”, “Pregnancy test” and “Platelet aggregation evaluation” eCRF pages (LBDTC variable from LB SDTM domain to be used)
 - Vital signs using information from “Vital signs” eCRF page (VSDTC variable from VS SDTM domain to be used)
 - Performance status using “ECOG Performance status” eCRF page (QSDTC variable from QS SDTM domain to be used)
 - ECG, using information from “Triplicate 12-lead electrocardiogram” (EGDTC variable from EG SDTM domain to be used)
 - Tumor assessments using “Tumor assessments” eCRF pages (TRDTC/TUDTC variable from TR/TU SDTM domain to be used)
 - Study maintenance assessments (XXDTC variable from XX SDTM domain to be used)
- Start and end dates of concomitant medications or anti-cancer therapies administered after study treatment discontinuation using “Concomitant medications”, “Anti-cancer treatment after discontinuation details” eCRF pages (CMSTDTC and CMENDTC variable from CM SDTM domain to be used)
- AE start and end dates using “Adverse events details” eCRF page (AESTDTC and AEENDTC variables from AE SDTM domain to be used)
- Study treatment administration dates using “MSCA2490484A Administration”, “Radiotherapy Administration” and “Cisplatin Administration” eCRF pages (EXSTDTC variable from EX SDTM domain to be used)
- Macroscopic signs of bleeding using “Macroscopics signs of bleeding” eCRF page (CEDTC or FADTC from CE/FA SDTM domains)
- Survival follow-up dates using “Survival Follow-up page” (YFSTDTC variable from YF SDTM domain where YFTESTCD=“SURVSTAT”).

In addition, waterfall plot representing the best percentage change in tumor size from baseline per subject will be provided. The unconfirmed BOR will also be presented as an annotation on each vertical bar.

15 Safety Analyses

The subsections in this section include specifications for summarizing safety endpoints that are common across clinical trials such as adverse events, laboratory tests and vital signs.

The primary endpoint of the Phase Ia is the occurrence of a DLT for a subject during the DLT observation period (5 weeks after the start of RT for Arm A and 12 weeks after the start of RT for Arm B). Based on the data observed, a recommendation of the next dose level is based on a Bayesian dose escalation design using a two-parametric logistic regression model. More details about the analysis to be provided to SMC members are presented in a dedicated IAP.

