- a. All subjects will be followed up for response until 12 months after the last subject has stopped RT/CRT, or earlier due to any reason whereby tumor assessments are no longer applicable (e.g., if a new treatment is started, withdrawal of consent). The reason for early discontinuation should be captured in the source document. If EOT occurs before PTD 365, all assessments must be done as planned for PTD 365. After completing the PTD 365 visit, subjects will be followed up for survival via phone call every 3 months, wherever possible.
- b. RT to be given 1.5 hours (\pm 30 minutes) after dosing.
- c. FD10 is the day of the last dose of RT. In case of premature withdrawal from the trial during the treatment period, the investigations scheduled for the visit on FD10 should be performed. In such cases this visit will be considered the Early Treatment Termination visit. If FD10 is on a Friday, PK, PD, safety laboratory, and urinalysis sampling must be done on FD9.
- d. All AEs will be collected from FD1 up to PTD 21 to evaluate the occurrence of DLTs.
- e. Hepatitis B and C testing to be performed at Screening unless obtained within 3 months prior to Screening. Screening for HIV will be performed according to local practice and local regulatory guidance.
- f. Heart rate, diastolic and systolic blood pressure, body temperature, and body weight. See Section [7.4.4](#) for details.
- g. Height measured at Screening only.
- h. Only required if subject has not started a new antitumor treatment. If a new treatment is started, the date (and regimen) must be reported in the eCRF.
- i. Physical exam will report findings in the irradiated area during all FU periods.
- j. Evaluation of ongoing treatment-emergent adverse events.
- k. See [Table 15](#) for details of hematology tests.
- l. See [Table 15](#) for details of serum chemistry tests.
- m. Urinalysis: dipstick followed by microscopic examination if abnormal results.
- n. 12-lead resting ECG in triplicate.
- o. 12-lead ECG to be performed predose and once at 2 to 3 hours postdose.
- p. 12-lead ECG to be performed at 2 hours postdose.
- q. Tumor imaging by CT or MRI at baseline to document extent of lesions according to RECIST v1.1. Baseline tumor evaluation can be up to 28 days old when treatment starts.

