6.6.2 Prohibited Medicines

As stated in Section [5.3.2](#), subjects must not have received chemotherapy, immunotherapy, hormonal therapy, biologic therapy, or any other anticancer therapy or any investigational agent

within 28 days of the first dose of IMP administration (6 weeks for nitrosoureas or mitomycin C), except for subjects with rapidly growing tumors localized in the head and neck region or thorax where the treating physician cannot wait for 28 days. These therapies are also prohibited during the treatment period and up to 30 days after RT, with the exception of concurrent cisplatin in the SCCHN population (Arm B). During the treatment period and up to 30 days after RT, any other investigational agent, chemotherapy, extensive RT (involving $\geq 30\%$ of bone marrow) or any other anticancer therapy (biologics or other targeted therapy) and antineoplastic steroid therapy are also prohibited (Phase Ia and Phase Ib only). Use of any investigational agent during the entire trial duration is not permitted.

Medications or herbal supplements known to be potent inhibitors or inducers of CYP3A or CYP2C19, or drugs mainly metabolized by CYP3A with a narrow therapeutic index as judged by the Investigator (and after optional consultation with the Sponsor) are prohibited (see Section 6.6.4 for details).

The solubility of M3814 is pH dependent; therefore, antacid drugs, H₂-blocker and PPIs might affect absorption. H₂-blockers or PPIs should be stopped 5 days prior to the first treatment, and avoided during the entire treatment period with IMP. Antacid drugs should not be taken 1 hour before IMP administration until 2 hours after IMP administration.

If the administration of a nonpermitted concomitant drug becomes necessary during the treatment period, e.g., due to AEs, the subject should be discontinued from the trial treatment and complete all assessments listed under the ETT visit.

See also Section 6.6.4 for details of possible drug-drug interactions with and by concomitant medication.

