7.1.3.5 Long-term Safety Follow-up: Phase Ia and Phase Ib

The following assessments will be performed for all subjects, excluding subjects in the ancillary cPoP part of the trial, on PTD 42, 126, 168, and 180, (Phase Ia and Phase Ib), and on PTD 270 and 365 (Phase Ib only):

- Assessment of vital signs (blood pressure, heart rate, and body temperature), body weight
- Physical examination
- 12-lead ECG including QTcF (Arm B SCCHN cohort only)
- ECOG PS
- Evaluation of all tissues in the RT area
- Evaluation of ongoing TEAEs
- Tumor assessment according to RECIST v1.1, only required if subject has not started a new antitumor treatment. If a new treatment is started, the date (and regimen) must be reported in eCRF.

The following assessments will be performed on PTD 210 and 312:

- Evaluation of long term RT toxicity (subject called by phone).

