7.1.3.6 Survival Follow-up: Phase Ia and Phase Ib

The following assessments will be performed on PTD 270 and 365 (EOT) for patients in Phase Ia, Arm A:

- Assessment of vital signs (blood pressure, heart rate, and body temperature), body weight. Only required for Phase Ia if subject has not started a new antitumor treatment
- Physical examination
- ECOG PS

- Evaluation of all tissues in the RT area
- Evaluation of ongoing TEAEs
- Tumor assessment according to RECIST v1.1. Only required for Phase Ia if subject has not started a new antitumor treatment.

For all patients, the survival follow-up period will continue until 12 months after the last subject has stopped RT/CRT (defined as end of trial; see Section 5.7). After completion of the visit on PTD 365, all subjects will be followed for survival every 3 months via a phone call until the end of the trial.

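### SAP 14.1 does not carry over the protocol's new-treatment limit, so a scan after new anticancer therapy but before PD can count toward Phase Ia best overall response

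*SAP*

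**What the plan says.** **SAP.** Section 14.1 defines BOR as the best RECIST 1.1 response up to first PD or the data cut-off. It names one treatment-based exclusion: the derivation is made "using the Investigator reported overall response per time point and excluding assessments after tumor surgery". Surgery is the only later treatment that removes a scan. Confirmed BOR needs a second assessment at least 4 weeks after the first, and the table footnote says this need not be the very next scan. ORR and DCR are derived from BOR with exact Clopper-Pearson intervals. The waterfall plot shows the best percentage change in tumor size from baseline, with no window stated beyond the general cut-off rule in section 9.

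New anticancer drugs, surgery and radiotherapy appear in section 12.5 only as listings: "Anti-cancer post-treatments will be listed according to eCRF page". Section 7, which declares departures from the protocol's planned analyses, does not mention the point.

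**Protocol.** Footnote a of Tables 1, 2 and 5 ends response follow-up early for any reason "whereby tumor assessments are no longer applicable (e.g., if a new treatment is started, withdrawal of consent". Section 7.1.3.5 makes the long-term tumor assessment "only required if subject has not started a new antitumor treatment", and section 7.1.3.6 has the same condition for Arm A at PTD 270 and 365: "Only required for Phase Ia if subject has not started a new antitumor treatment". The date and regimen of the new treatment must be entered in the eCRF. On other anticancer therapies, section 6.6.2 says: "These therapies are also prohibited during the treatment period and up to 30 days after RT".

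**The concern.** The SAP accepts that a later treatment can confound response, since it drops scans after surgery, but it stops there. Protocol section 3.2 describes Arm A disease as not amenable to surgery, so a new drug or a further course of radiotherapy is the more likely confounder in that arm.

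BOR, ORR, DCR and the tumor-size plots are the Phase Ia evidence on antitumor activity, and SAP section 4 says the planned analyses will go into the trial report and into regulatory submissions or manuscripts. If a response produced by next-line therapy enters these outputs, it is read as activity of the trial combination at a given dose level.

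**Working it through.** The plan states no figure to reproduce here. The check has four steps.

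**1. Can new therapy precede a scheduled scan?** Table 1 footnote r gives four scans in Day 31–180 and two in Day 181–365. The visit days are PTD 42, 84, 126, 168 (4) and 270, 365 (2). The ban on other anticancer therapy ends 30 days after RT. With the ±7-day visit window the earliest first scan is PTD 42 − 7 = PTD 35, and 35 > 30. All six scans fall after the ban, so new therapy could precede any of them. This shows opportunity, not frequency.

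**2. Does the protocol stop such scans from being entered?** Not fully.
- Sections 7.1.3.5 and 7.1.3.6 say when a scan is required. They do not forbid a later one.
- Section 7.1.3.5 lists PTD 42, 126, 168 and 180 for Phase Ia. PTD 84 comes under section 7.1.3.4, which does not state the exemption. As Tables 1 and 2 read, footnote h (the exemption) is on the long-term and survival tumor-assessment cells but not on the mid-term PTD 84 cell.
- Table 5 (Arm B) has no such footnote on its tumor-assessment row. Only footnote a and the text of 7.1.3.5 carry the limit.

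**3. What does the SAP rule do with such a scan?**
- *New response.* No PD so far, new drug started after PTD 30, PR entered at PTD 84. The scan is before PD and not after surgery, so BOR = PR.
- *Confirmation.* PR at PTD 42, new therapy between the two scans, PR at PTD 84. The gap is 84 − 42 = 42 days, above 4 weeks (28 days), so confirmed BOR = PR.
- *New therapy after documented PD.* The scan is outside BOR. It is not outside the waterfall plot as worded.

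**4. Size of one such response.** The ORR denominator is the analysis set (SAP section 9), so adding scans cannot lower ORR. One response is worth 1/n. Inputs for n: 3 per cohort (Protocol 5.1.1); up to 6 per tablet dose level (5.1.2); 12 if four cohorts share a dose, because SAP section 9 pools same-dose cohorts and escalation stops once more than three cohorts share a level (4 × 3 = 12); and 30, the escalation maximum. The response counts are illustrative.

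| n | With the scan: ORR (exact 95% CI) | Scan excluded: ORR (exact 95% CI) | Change, points |
|---|---|---|---|
| 3 | 1/3 = 33.3% (0.8–90.6) | 0/3 = 0% (0–70.8) | 33.3 |
| 6 | 2/6 = 33.3% (4.3–77.7) | 1/6 = 16.7% (0.4–64.1) | 16.7 |
| 12 | 3/12 = 25.0% (5.5–57.2) | 2/12 = 16.7% (2.1–48.4) | 8.3 |
| 30 | 9/30 = 30.0% (14.7–49.4) | 8/30 = 26.7% (12.3–45.9) | 3.3 |

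With no such scans the change is zero.

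**The case against.** The best defence is that the protocol handles this at collection. Response follow-up ends when a new treatment starts, so few or no such scans should reach the database, and nothing in the documents shows that sites enter them. Investigational agents are barred for the whole trial (Protocol 6.6.2), and joining another trial means withdrawal (5.5.2), which narrows the pool to non-investigational therapy. BOR already stops at first PD, which takes out most next-line treatment. Phase Ia activity is a secondary, exploratory objective with no test or threshold, and with 3 subjects the interval is too wide to inform in either case. By-subject listings of later therapies and of imaging dates let a reader trace a doubtful response.

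Most of this stands as a limit on size. It does not close the gap, because a scan that is not required can still be done and entered, and the SAP text then counts it. Tracing it afterwards through listings would leave the decision to be made with the results in view.

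A reader might go further and infer that SAP 14.1 removes post-surgery scans and nothing else, that any response after new therapy is credited to the trial treatment, or that the SAP contradicts the protocol. The documents do not support these readings. Scans after first PD and after the cut-off are also outside BOR. Misattribution needs new therapy before PD, a scan that is still entered, and a better or confirming result on it. The SAP leaves out a limit that the protocol sets; it does not order scans against it.

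**Conclusion.** The gap is real and worth closing, but its effect is conditional. As written, a scan entered after a new anticancer drug or new radiotherapy and before documented PD can create or confirm a response in Phase Ia, and the waterfall plot can also show shrinkage after PD, surgery or new therapy.

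Any effect on ORR is upward or nil. The figures above are per affected subject and assume at least one. The documents give no number of affected subjects, so it cannot be said that the reported ORR is inflated.

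It would also be wrong to extend the point to dose-limiting toxicity, which does not use BOR, or to the Phase Ib response rate, for which the SAP says a separate plan will be issued.

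**What to change.** In SAP 14.1, replace the surgery exclusion with: *excluding assessments after the start of any new anticancer drug therapy, anticancer radiotherapy or tumor surgery, whichever is first*. Then:

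- apply it to unconfirmed and confirmed BOR, ORR and DCR;
- apply it, together with the PD limit, to the waterfall plot;
- mark the start of new therapy on the spider and swimmer plots.

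The start dates come from the post-discontinuation anticancer eCRF pages named in SAP 12.5. Protocol 7.1.3.5 already requires the date of a new treatment to be reported.

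The cost is one sentence and one derivation condition, with no new data. ORR may be slightly less favourable. A response seen before new therapy but re-scanned only after it will count as unconfirmed. Scans after radiotherapy to an unrelated site also drop out. These are choices about what response is meant to measure, so they are better written down before the final database lock. If no such scans exist, BOR, ORR and DCR do not change.
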